6.2.4. Post-treadmill test examination

After completing the treadmill tests, patients will undergo a control ECG examination to exclude ischemic changes in the myocardium and cardiac arrhythmias..

6.3. Length of prospective observation

The effects of the treatment will be assessed within three months. It is assumed that the observation period can be extended to a maximum of 12 months.

6.4. Endpoints of the study

The endpoints of this study and the complications were developed in accordance with the results of the COMPASS study. Parameters related to the results of the treadmill test were added. The study endpoints are summarized in Table 6. The complications related to possible bleeding risk for PAD patients are presented in Table 7.

Table 6. Endpoints of the study

Parametr	Study
Primary outcomes	
Rate of stroke	COMPASS
Rate of myocardial infarction	COMPASS
Rate of cardiovascular death	COMPASS
Rate of death	COMPASS
Prespecified limb outcomes	
Rate of acute limb ischaemia	COMPASS
Rate of major amputation	COMPASS
Rate of all vascular amputations	COMPASS
Treadmill tests outcomes	
Change in the distance of intermittent claudication in the test according to Gardner's protocol (ΔD_{ch} ; ΔD_{max}).	This study
Change in the value of oxygen uptake (ΔVO_{2max})	This study
Change in energy expenditure expressed as the metabolic equivalent of MET-s ($\Delta MET-s$)	This study

Table 7. Safety outcomes for patients with PAD

Parametr	Study
Rate of major bleeding	
Rate of fatal bleeding	COMPASS
Rate of non-fatal symptomatic intracranial haemorrhage	COMPASS
Rate of non-fatal, non-intracranial haemorrhage symptomatic bleeding into a critical organ	COMPASS
Rate of other major bleeding (surgical site bleeding requiring reoperation or bleeding leading to hospitalization)	COMPASS
Rate of fatal or symptomatic bleeding into a critical organ	COMPASS
[Rate of fatal or symptomatic bleeding into a critical organ or surgical site bleeding leading to re-operation]	[COMPASS- not used in this study]
Rate of ISTH major bleeding	COMPASS
Sites of bleeding (frequency of occurrence)	
Gastrointestinal	COMPASS
Intracranial	COMPASS
Genitourinary	COMPASS
Ocular	COMPASS
Skin	COMPASS
Respiratory	COMPASS
Other	COMPASS
Minor bleeding	COMPASS

6.5. Biological samples

6.5.1. Biological material collection - blood samples

For standard diagnostic and molecular tests, fasting venous blood samples will be taken from the ulnar vein in the volume of 9-27 ml, from a single puncture. Samples will be collected after the patient is qualified for tests (**1 collection during the study**).

Subsequent samples of venous blood from the ulnar vein (10 ml) and capillary blood from the fingertip (1 ml) will be collected during treadmill tests before and after the exercise to determine objective metabolic markers associated with the exercise (**a total of 2 venous and 2 capillary blood collections during the tests**).

Blood collection from the ulnar vein is a standard invasive test that causes about 1 minute of discomfort and pain, and the risk of bruising, redness, or skin infection is very low. Whenever possible, to reduce the discomfort, additional blood samples will be taken when other routine laboratory diagnostic tests are carried out.

Blood samples may be taken: at the wards of the Department of Vascular and Endovascular Surgery, Angiology and Phlebology of the PUMS at the blood collection point of the The Lord's Transfiguration Clinical Hospital of PUMS or the Department of Physiology and Biochemistry of the University of Physical Education by researchers or collaborators. As compensation, the examined persons will receive free of charge the results of additional laboratory tests conducted by the investigators. If it is not possible to collect blood from the ulnar vein, the blood will be collected from another location (wrist, hand) with the consent of the examined person. The capillary blood from the pad also causes short (30 s) pain and discomfort to the patient, and the risk of bruising, redness, or skin infection is very low in this case.

6.5.2. Preparation and storage of blood samples

Blood samples will be used to perform laboratory tests (9 ml, The Lord's Transfiguration Clinical Hospital Central Laboratory) and to obtain material for further biochemical and molecular analyses: plasma/serum and genomic DNA (residual blood; **Table 8**).

Table 8. Use of biological material

LP	Biological material	Analyses
1	Plasma / peripheral fasting blood serum	• Assessment of blood biomarker concentrations
2	Morphotic elements of peripheral blood	• Isolation of genomic DNA, genetic analysis
3	Plasma / peripheral blood serum before and after exercise	• Biochemical analysis - effort markers
4.	Krew kapilarna przed i po wysiłku	• Capillary blood before and after exercise

Serum samples (fasted venous blood) will be collected in serum-separating tubes containing a serum accelerator (SST; proposed: S-Monovette Serum Z, manufacturer of SARSTEDT), left to clot for 15 minutes at room temperature or overnight at 4°C and then centrifuged at 1000 x g for 15 minutes. The serum will be divided into 500 µl samples, placed in 1.5 ml Eppendorf tubes and stored at -80°C.

Blood samples for plasma collection (venous blood collected on an empty stomach) will be collected using the sodium version, EDTA, as an anticoagulant (S-Monovette EDTA,

manufacturer of SARSTEDT), centrifuged for 15 minutes at 1,000 x g at 2-8°C within 30 minutes of collection. Part of the plasma will then be centrifuged for 15 minutes at 4000 x g (for blood micro RNA levels). The plasma will be divided into 500 µl samples, placed in 1.5 ml Eppendorf tubes and stored at -80°C. The remainder of the blood sample taken on EDTA, which contains all cellular elements, will be used for DNA extraction.

Twice during each test, i.e., at rest and after exercise, approximately 10 ml of blood will be taken from the ulnar vein using an S-Monovette syringe without anticoagulant (made by SARSTEDT, Germany), then centrifuged (1500 g, 4°C, 4 minutes) to separate the serum and plasma. The samples will be frozen at -80°C pending biochemical analyses. Similarly, twice during each test

Capillary blood samples will be analyzed immediately after collection.

All samples (blood, fractions obtained) will be stored in the Department of Vascular Surgery, Endovascular Surgery, Phlebology and Angiology of the Medical University of Poland, Department of Physiology and Biochemistry of the University of Physical Education and the Institute of Human Genetics of the Polish Academy of Sciences in Poznań.

6.5.3. Material and methods for laboratory testing of patient blood

The results of laboratory tests will be performed in the Lord's Transfiguration Clinical Hospital Central Laboratory. These results will come from available clinical documentation or will be performed in the above mentioned Laboratory based on a separate agreement with the Hospital. It is also acceptable for the patient to pay for the tests themselves. The analyses will be carried out using standard laboratory techniques used in the Lord's Transfiguration Clinical Hospital Central Laboratory.

6.5.4. Biochemical blood tests

The concentration of lactate in capillary blood before and after exercise (assessment of the metabolic severity of exercise acidosis) will be tested using EDGE Blood Lactate Test Strip, ApexBio, (Taiwan) based on the analysis of blood taken from the fingertip. Similarly, venous blood will be collected before and after exercise for biochemical tests, including gasometry.

6.5.5. Material and methods for testing peripheral blood biomarkers

The level of selected proteins in the blood will be assessed by the immunoenzymatic method (ELISA). The assays of selected circulating miRNAs will be performed using TaqMan (Life Technologies) using the 7900HT Fast Real-Time PCR System (Life Technologies). These tests will be performed at Institute of Human Genetics PAS.

Further analysis of biomarkers present in the blood, to obtain funds for testing, assumes the possibility of using high-pass transcriptomic (use of expressive microarrays) and proteomic (using mass spectrometry) methods.

6.5.6. DNA analysis

DNA extraction will be performed chemically using guanidine isothiocyanate, phenol, and chloroform to remove proteins.

Analysis of genotypes for selected SNPs, including genes with proven role in cardiovascular susceptibility (related to: response to hypoxia, angiogenesis, antioxidant barrier, lipid metabolism, homocysteine and hypertension). Among others, functional polymorphisms of genes *MTHFR*, *ApoE*, *HIF1A*, *VEGF*, *PONI*) will be assessed using allele discrimination tests (TaqMan SNP Genotyping Assays, Life Technologies) and 7900HT Fast Real-Time PCR System (Life Technologies) in at Institute of Human Genetics PAS.

Material is to be collected for mutation evaluation, whole exome/genome sequencing and epigenome studies. These studies will be carried out based on the DNA sequencing method using the apparatus available in Poznan University of Medical Sciences / Institute of Human Genetics PAS or external services.

Unique Protocol ID:

PAD_RIV_CLIDIS_PL

Title:

Influence of Rivaroxaban for Intermittent Claudication and Exercise Tolerance
in Patients With Symptomatic PAD

NCT number:

NCT04305028

Document date

02/13/2020

STATISTICAL ANALYSIS PLAN

1. Randomization

Due to the limited number of studied groups, randomization of patients will be carried out using the minimization or equivalent principle, which allows maintaining similarity of groups in terms of known prognostic factors.

The minimization principle by Taves (1974), independently developed and generalized by Pock and Simon (1975), takes into account the previous distribution of patients with specific prognostic factors in particular groups. It is based on the algorithm of assigning another patient to one of the arms in such a way as to reduce the total differentiation of groups with respect to selected features. The following parameters will be taken into account as stratifying factors: age (<65 vs. ≥65), gender (women vs. men), degree of disease (Fontaine IIa vs. IIb scale), diabetes (yes vs. no), current smoking (yes vs. no). The number of analyzed factors is consistent with the recommendations of the authors, who recommend including no more than five stratifying factors. The advantage of minimization is the fact that it is a "dynamic" method, which does not require prior preparation of randomization lists but allows to select treatment "on the fly" on the basis of updated data analysis.

In order to carry out the randomization, a calculator and database have been developed, which will be available online for cooperating physicians (Fig. 1 and 2). This will allow for real-time randomization by researchers, including patients in the study at the same time. The prototype table contains personal data, while the final version will provide anonymized data.

Figure 1. The calculator developed for randomization.

		Treatment A	Treatment B
Parameter	Value	ASA	ASA+ Xarelto
Age	<65	1	0
	≥65	0	0
Sex	W	0	0
	M	0	1
Fontaine Scale	IIa	0	1
	IIb	0	0
Diabetes	Yes	1	0
	No	0	0
Current smoking	Yes	1	0
	No	0	0
Number of cases		0,6	0,4
Age	≥65	1	1
Sex	M	0	2
Fontaine Scale	IIa	0	2
Diabetes	Yes	0	0
Current smoking	No	0	0
Variability of features		1	5
RESULT OF RANDOMIZATION	Drug	ASA	

Figure 2. The database used to perform randomization.

	A	B	C	D	E	F	G	H	I	J	K	L
	LP	Patient ID	Initial	Date of recruitment	Age	Sex	Fontaine Scale	Diabetes	Current smoking	Pharmacotherapy	Physician	Case

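### SAP section 1 puts the minimisation counts and the allocation list online in an open single-centre trial, with no stated lock before the arm is released, random element or tie rule

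*SAP*

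**What the plan says.** Protocol section 4 describes the study as open, randomised and single-centre. Protocol section 5.4 says only that patients are allocated at random to the two groups.

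The detail is in SAP section 1:

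- **Method.** Allocation is made "using the minimization or equivalent principle", with five two-level factors: age, sex, Fontaine grade, diabetes and current smoking. Each new patient goes to the arm that lowers the total imbalance between groups, chosen "on the basis of updated data analysis".
- **Access.** The SAP states that "a calculator and database have been developed, which will be available online for cooperating physicians". It adds: "This will allow for real-time randomization by researchers".
- **What the tool holds.** Figure 1 shows counts by arm at each factor level, a total for each arm labelled "Variability of features", and one resulting drug. Figure 2, captioned "The database used to perform randomization", lists patients with their five factors and a pharmacotherapy column.
- **Stated safeguard.** "The prototype table contains personal data, while the final version will provide anonymized data".

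Neither document states a step that withholds the arm until the patient is irrevocably registered, a bar on recruiters seeing the counts, a probability of assigning the favoured arm, or a rule for ties.

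**The concern.** In an open trial, concealing the next allocation is the main protection against selective enrolment. A recruiter who can foresee the arm can decide whether and when to enter a patient, and can do so on traits outside the five factors. Minimisation cannot correct for that.

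The inputs needed to work out the next arm are the counts by arm at each factor level and the new patient's five factors. SAP section 1 places the first online and names no point at which the second must be fixed before the result appears. Anonymising the table hides who the earlier patients are; it does not hide which arm they received.

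**Working it through.** The plan gives no predictability figure to reproduce, so the check is a simulation of the rule it describes. The sample size calculation in SAP section 2 plays no part in this point.

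**Inputs from the SAP.** N = 60 with 30 per group, and a ceiling of 100 (section 2); five two-level factors (section 1).

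**Assumptions.** The factors are independent and equally weighted, with prevalences of 0.3 to 0.5. Ties are split 50:50. The documents give none of these.

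**Rule.** For factor k, let d_k be the ASA count minus the ASA + rivaroxaban count at the new patient's level. The score for ASA is the sum over the five factors of |d_k + 1|; the score for ASA + rivaroxaban is the sum of |d_k − 1|. The lower score marks the favoured arm. Deterministic means that it is always given; the 0.80 coin means that it is given with probability 0.80.

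**Results at N = 60, share of arms guessed correctly:**

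| What the guesser knows | Deterministic | 0.80 coin |
|---|---|---|
| All counts and the patient's five factors | about 91-92% | about 75% |
| Arm totals only | about 72% | about 64% |
| All patients' factors, but not the arm of 10% of past patients (unknown arms filled in by the rule) | about 83-86% | about 67-69% |

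**Hand check of the first row.** Under the deterministic rule about 17% of allocations are ties (0.17 × 60 ≈ 10 patients) and 83% are fully determined. Correct guesses are 0.83 + 0.17 × 0.5 = 0.915. With the coin, ties are about 15%, so the figure is 0.85 × 0.80 + 0.15 × 0.5 = 0.755.

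**At N = 100** the first two rows are much the same: 92% / 75% and 72% / 64%. A larger trial does not make the next arm less predictable to someone who sees all counts.

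**Effect of hiding the counts.** This depends on what staff still know. If 10% of past records are wholly missing and the guesser simply scores the rest, the figures are 69-70% / 64-65%. If only the arm is missing for the same 10%, they are 83-86% / 67-69%, as in the table. No fixed range after the fix can be given.

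**Effect of the coin on balance at N = 60.** The mean gap in diabetes prevalence between arms goes from about 2.7 to about 4.5 percentage points, against about 10 under simple randomisation. The mean difference in arm size goes from 0.3 to 1.0 patients.

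**The case against.** **The live tool may be better protected than the plan says.** The SAP itself separates a prototype table from a final version, and access settings often sit in an operating procedure. This stands. A reader might infer from section 1 that recruiters will in fact see the next arm, but the documents do not show that. They show access granted in general terms and no stated restriction.

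**The 91-92% figure needs several conditions at once.** The rule must be deterministic, the guesser must see live counts and know all five factors, and must still be free to defer or decline the patient. This also stands, and is why the figure is an illustration. The deterministic reading is nevertheless the natural one: the text says the arm is chosen to reduce imbalance, and Figure 1 turns totals of 1 and 5 into the single result ASA. The 0.6 and 0.4 beside "Number of cases" are not assignment probabilities. They are the column sums divided by the five factors: 3/5 and 2/5.

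**If the rule is deterministic, adding a coin changes the design and does not fill a gap.** That is fair, and it is put forward as such. The lock, the restricted view and the tie rule are gaps on either reading.

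**Cooperating physicians may not be recruiters.** Protocol section 5 uses the phrase for those who refer patients; the SAP uses it for those given the tool. That they are the same people is not stated. The SAP does say, however, that researchers randomise at the time they include patients, so enrolling staff use the tool on its own wording.

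**Two further readings go beyond the documents.** One is that the results will be biased by a known amount or in a known direction; nothing in either document supports such a figure. The other is that the worked example in Figure 1 shows faulty live allocations; it is an example screen and cannot show that.

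**Conclusion.** The concern holds as a weakness of the written plan. Followed as written, SAP section 1 permits the next arm to be foreseen: counts and past arms are online, the rule reads as deterministic, and nothing stated fixes the patient's entry before the arm appears. Under the stated assumptions, full sight of the counts makes about nine arms in ten predictable, against about three in four with a 0.80 coin. About one allocation in six has no written rule because it is a tie.

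These figures rest on independent, equally weighted factors and assumed prevalences. The plan does not establish that allocation will be predictable in practice, and no effect on the treatment comparison or the type I error is claimed. The change should be made because it is cheap and this is an open trial.

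**What to change.** Add to SAP section 1:

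1. Eligibility, consent and the five factors are entered and locked, and the patient is irrevocably registered, before the system releases the arm. Recruiting and referring physicians see neither the running counts nor the allocation list.
2. The scoring rule and factor weights are stated, ties are split 50:50, and the favoured arm is assigned with a stated probability below 1 (for example 0.80; the value is the sponsor's choice).

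The second part supports the first: in a single-centre open trial, staff who treat enrolled patients will still know some past allocations. Test the calculator on cases covering all five factors before first use.

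The cost is one paragraph, access settings on the online tool and a short test run, with no extra patients or visits. Balance loosens slightly, as shown in the working, and stays well inside that of simple randomisation. If the final tool already has these controls, recording them is enough for the first part.

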Population Mean μ_1		3,6670		
Population Mean μ_2		-1,3330		
Population S.D. (Sigma)		5,8000		
Standardized Effect (Es)		0,8621		
Type I Error Rate (Alpha)		0,0500		
Critical Value of t		2,0017		
Power Goal		0,9000		
Actual Power for Required N		0,9071		
Required N (per group)		30,0000		

b)

		Sample Size Calculation Two Means, t-Test, Ind. Samples H0: $\mu_1 = \mu_2$		
		Value		
Population Mean μ_1		3,6670		
Population Mean μ_2		-1,3330		
Population S.D. (Sigma)		11,6000		
Standardized Effect (Es)		0,4310		
Type I Error Rate (Alpha)		0,0500		
Critical Value of t		1,9704		
Power Goal		0,9000		
Actual Power for Required N		0,9023		
Required N (per group)		115,0000		

If a statistically significant effect (80-90% test power) cannot be achieved with the assumed sample size, the test protocol will be modified by increasing the sample size and/or extending the observation period. For estimation of the sample size, the relationship between the test power and sample size will be analyzed. The results of such an analysis for the sample values contained in Figure 3a are given in Figure 4.

Figure 4: Example of a graph of test power versus sample size. Data for the example in Figure 3a

It is assumed that the study group will not exceed 100 participants (50 in each group), and the observation period will be extended to a maximum of 12 months. In the absence of significant results for extended observations, interpretation of the data will be based on indicating that it is impossible to reject the zero hypotheses (H0) that the tested drug does not affect the progress of the disease, with the indicated statistical power of the study.

The analysis of test power and sample size will be carried out using the module "Test Power Analysis" of STATISTICA v10.0.

3. Statistical analysis of the results

Statistical evaluation of the results will be carried out using standard statistical methods, single- and multi-factor tests. These analyses will be carried out using STATISTICA v10.0 and GraphPad Writings programs. Hypotheses will be verified at the significance level $P < 0.05$. The evaluation of genotypes will take into account the Bonferroni correction for multiple comparisons.

LITERATURE

